9.4.5 Secondary Endpoints

9.4.5.1 Timed Function Tests

[figure not shown]
Timed function tests (10-meter run/walk, 4-stair stair-climb, and 4-stair stair descend) will be analyzed using the analysis methods outlined for the primary efficacy variable (MMRM and ANCOVA), for both the mITT and ITT populations, at the end of the double-blind and open-label phases. A separate analysis will evaluate 10-meter run/walk results in subjects with a baseline 6MWD <300 meters. An additional analysis will evaluate a composite endpoint of average change in times to run/walk 10 meters, climb 4 stairs, and descend

4 stairs. Subjects who cannot perform a timed function test within 30 seconds will be assigned a value of 30 seconds for the analysis.

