9.2.2 Modified Intention-to-Treat (mITT) Population

This population will include all subjects in the ITT population who meet the following additional criteria: ≥ 7 to ≤ 16 years old with 6MWD ≥ 300 meters and time to stand from supine ≥ 5 seconds at baseline. This population will be used for the primary endpoint analysis, and other supportive analyses.

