9.4.5.3 North Star Ambulatory Assessment

The NSAA consists of 17 activities, each scored as 0, 1, or 2. The sum of these 17 scores will be used to form a total score. This total score will be analyzed using the ANCOVA analysis method outlined for the primary efficacy variable, for both the mITT and ITT populations, at the end of the double-blind and open-label phases. A separate analysis for the open-label phase will evaluate changes in total score in subjects with a baseline 6MWD ≥ 400 meters and < 7 years of age. Transformation of the total score to a linear scale [Mayhew 2013a] also will be performed. In addition, the odds of losing one or more of the NSAA items (score of 1 or 2 at baseline transitioning to a 0 score post-baseline) will be evaluated for ataluren versus placebo subjects using a risk ratio derived via re-sampling based analysis methods; the “lifts head” item will be excluded from this analysis because it does not fit the original construct of the NSAA based on Rasch analysis [Mayhew 2013a].

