3.1. Intention-to-Treat Population

The intention-to-treat (ITT) population defined in the double-blind treatment period SAP will be used for summary and analysis of open-label efficacy endpoints.

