8. CHANGES FROM THE PROTOCOL

Major changes to the planned analyses from the protocol are summarized as follows:

- NSAA total score will be calculated as the sum of the 16 scores (except for lifts head), instead of 17, based on Mayhew's publication [Mayhew 2013a].
- Slope of change in 6MWD over 144 weeks is removed from the list of secondary endpoints in section 2.3.2.
- Modified Intention-to-Treat (mITT) Population is removed from the list of study populations
- MMRM model was modified from a linear regression model to a MMRM model with visit time as a categorical variable to account for the nonlinearity of study data.

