9. VERSION HISTORY

This Statistical Analysis Plan (SAP) for study PTC124-GD-041-DMD is based on protocol version 4.0 (dated 21JUL2020).

| SAP Version | Approval Date | Description |
|-------------|---------------|---|
| 1.0 | 04APR2022 | Original version |
| 2.0 | 25SEP2023 | 
Summary of Changes:
 
To be aligned with the “Changes from Planned Analysis” SAP for the double-blind period:
 
1) mITT population removed throughout this SAP2) MMRM slope model replaced with MMRM categorical model as primary analysis method3) slope of change in 6MWD over 144 weeks removed from the list of secondary endpoints4) baseline disease severity category updated throughout this SAP 
Other changes:
 
5) analyses on time to 10% persistent worsening and 30meter drop from baseline in 6MWD were added as sensitivity analyses |

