* 2nd: Impute missing ending data using monotone statement with regression option and assuming MNAR using CCMV;

```
proc sort data=smwt_mono out=smwt_mono; by _imputation_ trtn usubjid; run;
proc MI data=smwt_mono out=smwt_ccmv minimum=0 nimpute=1 minmaxiter=5000
seed=93035;
  WHERE ITTfl="Y";
  BY _imputation_ trtn;
  VAR SmwdWKBL SmwdWK12 SmwdWK24 SmwdWK36 SmwdWK48 SmwdWK60 SmwdWK72 SmwdWK96
SmwdWK120 SmwdWK144;
  MONOTONE reg(/details);
  MNAR Model (SmwdWK12 SmwdWK24 SmwdWK36 SmwdWK48 SmwdWK60 SmwdWK72 SmwdWK96
SmwdWK120 SmwdWK144/Modelobs=CCMV);
run;
```

* 3rd: Create datasets for ANCOVA;

```
data smwt_reg;
  set smwt_ccmv;
  AWeek= 0; Avalimp=SmwdWK0; CFBimp=SmwdWK0-BL6mwd; output;
  AWeek=12; Avalimp=SmwdWK12; CFBimp=SmwdWK12-BL6mwd; output;
  AWeek=24; Avalimp=SmwdWK24; CFBimp=SmwdWK24-BL6mwd; output;
  AWeek=36; Avalimp=SmwdWK36; CFBimp=SmwdWK36-BL6mwd; output;
  AWeek=48; Avalimp=SmwdWK48; CFBimp=SmwdWK48-BL6mwd; output;
  AWeek=60; Avalimp=SmwdWK60; CFBimp=SmwdWK60-BL6mwd; output;
  AWeek=72; Avalimp=SmwdWK72; CFBimp=SmwdWK72-BL6mwd; output;
  AWeek=96; Avalimp=SmwdWK96; CFBimp=SmwdWK96-BL6mwd; output;
  AWeek=120; Avalimp=SmwdWK120; CFBimp=SmwdWK120-BL6mwd; output;
  AWeek=144; Avalimp=SmwdWK144; CFBimp=SmwdWK144-BL6mwd; output;
```

run;

...

* 4th: Conduct ANCOVA analysis on imputed datasets;

```
proc sort data=adsmwdimp out=adsmwdimp; by _imputation_; run;
ods exclude all;
proc mixed data=adsmwdimp method=REML;
  WHERE ITTfl="Y" and Aweek=144;
  BY _imputation_;
  CLASS Cortico Trtn C6mwd Stand;
  MODEL CFBimp=BL6MWD Trtn Cortico Stand C6MWD / CL;
  LSMEANS Trtn/ diff=control('0') cl alpha=0.05;
  ods output diffs=diff_mi lsmeans=lsm_mi;
run;
ods exclude none;
```

* 5th: Use Proc MIAnalyze to obtain final analyiss results;

* LS Means;

```
proc mianalyze parms(classvar=full)=lsm_mi;
  CLASS Trtn;
  MODELEFFECTS Trtn;
  ods output parameterestimates=lsm_out;
run;
```

* Treatment differences;

```
proc mianalyze parms(classvar=full)=diff_mi;
  CLASS Trtn;
  MODELEFFECTS Trtn;
  ods output parameterestimates=diff_out;
run;
```

The table below lists the random seeds to be used for the primary and secondary analyses and some additional seeds should they be required. The random seeds were created using SAS uniform generator RAND(“Uniform”) with a seed of 20220316.

| Endpoint/Analysis | Seed for Step 1 (impute missing interim data) | seed for Step 2 (impute missing ending data) |
|--|---|--|
| 6MWD (mITT, Section 6.2.1) | 91137 | 7262 |

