3.5. Analyses for Overall Treatment Period

Since this study is still ongoing at the time of the first database lock, more than 40% of the subjects have not completed the open-label period by the data cutoff date. Only summary statistics will be presented for all efficacy endpoints for this Study 041 CSR. Statistical modellings will be performed at the final database lock when all subjects have completed open-label period.

[figure not shown]
[figure not shown]

3.6. mITT Analysis

Since the mITT analysis did not meet its primary objective of capturing significant benefit only the results for primary efficacy endpoint, change from baseline in 6MWD over the 72-weeks double-blind period is shown in-text. All other preplanned mITT analyses for other endpoints are presented end-of-text for the purpose of this CSR.

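### Open-label SAP v2.0, written after the double-blind mITT results were known, drops the Week 144 mITT analyses of timed function tests and NSAA that the protocol requires

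*Protocol*

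**What the plan says.** **Protocol.** Section 9.2.2 defines the mITT as ITT subjects aged 7 to 16 with baseline 6MWD of at least 300 m and stand-from-supine time of at least 5 s, and gives its role: "This population will be used for the primary endpoint analysis, and other supportive analyses". Section 9.4.5.1 prescribes, for the timed function tests, "MMRM and ANCOVA), for both the mITT and ITT populations, at the end of the double-blind and open-label phases". Section 9.4.5.3 prescribes ANCOVA of the NSAA total score "for both the mITT and ITT populations, at the end of the double-blind and open-label phases".

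**Open-label SAP v2.0.** Section 8 lists as a departure: "Modified Intention-to-Treat (mITT) Population is removed from the list of study populations". The first v2.0 item in Section 9 reads "mITT population removed throughout this SAP", under a statement that the aim is alignment with the double-blind changes document. Section 3.1 says the ITT set "will be used for summary and analysis of open-label efficacy endpoints". The Week 144 models in Sections 6.2.1 to 6.2.3 and 6.3.1 are specified for ITT alone. Appendix 2 nevertheless still carries rows such as "6MWD (mITT, Section 6.2.1" in its seed table.

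**Double-blind changes document (Changes from Planned Analysis).** Section 3.6 keeps the mITT result for the primary endpoint in the body of the report and says of the rest: "All other preplanned mITT analyses for other endpoints are presented end-of-text for the purpose of this CSR". Section 3.5 limits that report to summary statistics for the overall treatment period and leaves modelling to the final lock.

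**The concern.** The population for which the trial was designed and powered disappears from the long-term analysis after its Week 72 result was seen. The changes document says openly, in Sections 1 and 3.6, that mITT was demoted because it failed to show significant benefit. A population removed for that reason, with no separate argument for Week 144, leaves a selective record.

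At stake is whether a reader can see if the small Week 72 mITT difference persists, shrinks or reverses by Week 144, when early start is compared with delayed start. Without these models the reader sees only the population that was moved into the lead once the data were known.

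**Working it through.** The point disputes no figure in the plan, so most of the check is a comparison of texts.

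**1. Size of the omitted population.** The double-blind SAP, Section 2.4, assumes a difference of 1.0 m/week, SD 2.058, two-sided alpha 0.05 and power 85%. Per arm, n = 2 × (1.960 + 1.036)² × 2.058² / 1.0² = 76.05, rounded up to 77, so 154 in total, as stated. Allowing for about 5% discontinuation, 154 × 1.05 = 161.7, which gives the stated 162 (154 / 0.95 would give 163). Against about 340 planned, 162 / 340 = 47.6%. The actual mITT count is not in the documents.

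**2. Timing.** Open-label SAP v1.0 is dated 4 April 2022, 7 days before the soft lock of 11 April 2022 (Section 1). Version 2.0 is dated 25 September 2023, 532 days after that lock. Removal throughout implies that v1.0 contained mITT analyses.

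**3. What was known.** Table 1 of the changes document gives Week 72 mITT differences (ataluren minus placebo) with standard errors. With z = estimate / SE and a normal approximation:

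| Model | Difference (SE), m | z | two-sided p |
|---|---|---|---|
| Prespecified slope MMRM | 9.95 (14.9) | 0.67 | 0.50 |
| ANCOVA after MI | 9.10 (13.1) | 0.69 | 0.49 |
| Categorical MMRM | 8.26 (9.1) | 0.91 | 0.36 |

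For the last row the approximate 95% interval is 8.26 ± 1.96 × 9.1, or −9.6 to 26.1 m. The SAP was revised with these results in hand.

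**4. Does the stated reason support deletion?** Version 2.0 cites alignment. The document it aligns with keeps one mITT result in the text and the others at the end of the report. That is relocation. Because it also defers overall-period modelling to the final lock, and v2.0 governs that lock without mITT, no document supplies a Week 144 mITT model.

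**5. Does anything else in v2.0 rebuild the mITT?** No. The severity subgroups in Sections 6.2.1.1, 6.2.2 and 6.2.3 use baseline 6MWD bands only and ignore age and stand time. They are also by-visit summaries, not models.

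**6. Leftovers.** Section 2.1 still describes the primary analysis as aimed at the mITT subset. The seed table has seven mITT rows: 6MWD, 10-metre run/walk, stair climb, stair descend, NSAA, PUL and PROM. The sections they cite no longer contain an mITT analysis. There is no row for the timed-function composite in either population.

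**The case against.** **ITT was not invented after unblinding.** True. Protocol 9.2.1 assigns ITT to efficacy analysis, and the same protocol sentences that require mITT at Week 144 require ITT there too. A reader might infer that the long-term conclusion rests on a set picked once the results were known. The documents support less: ITT was promoted, and at Week 144 left as the sole population.

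**The ITT estimate is not distorted.** Also true. A reader might try to calculate a bias from carrying forward the better-looking of two nested sets. The Week 144 ITT results for these endpoints were due in any case. Deleting mITT does not move them, and restoring it would not correct them.

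**The visible mandate is narrow.** It covers timed function tests and NSAA. The public protocol text shows no equivalent requirement for 6MWD, PUL, PROM or time-to-event endpoints. The seed rows for 6MWD, PUL and PROM show what was planned, not what the protocol demands.

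**Some mITT information may survive.** The first study report could hold overall-period mITT summaries among its end-of-report tables; the documents do not say. A claim that no mITT data beyond Week 72 will appear anywhere is therefore not established. Any such summaries would be partial, since more than 40% of subjects had not finished the open-label period at the cutoff.

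**The change is disclosed and the endpoints are secondary.** Sections 8 and 9 declare it, Section 2.3.1 has no primary endpoint for this period, and Section 4.7 applies no multiplicity control. This limits the consequence, but disclosure does not supply the missing results.

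**Conclusion.** The departure is real. Protocol-required Week 144 mITT analyses of the timed function tests (MMRM and ANCOVA) and NSAA (ANCOVA) were removed after the mITT results by arm were available, on a justification that does not support removal. The consequence is selective omission of the protocol's primary population, about 48% of planned enrolment, from the long-term secondary results.

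It is not a confirmatory type I error, because no Week 144 test is confirmatory, and no bias figure for the ITT estimate should be attached to it. The conclusion rests on the dates and texts above and on the inference that v1.0 contained mITT analyses, which its removal throughout v2.0 and the surviving seed rows both support. The 48% uses planned numbers.

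**What to change.** Issue a new open-label SAP version and leave the v2.0 history entry intact, since it records what that version did. In the new version:

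- Restore mITT as a supportive population in Section 3, withdraw the removal bullet in Section 8, and reconcile Section 2.1 and the Appendix 2 rows with the result.
- In Sections 6.2.2 and 6.2.3, add the Week 144 mITT MMRM and ANCOVA for the timed function tests and the mITT ANCOVA for NSAA. Add 6MWD in Section 6.2.1 for consistency.
- Adapt the models to the population. Every mITT subject has a stand time of at least 5 s and a 6MWD of at least 300 m, so omit the stand-time factor (as the double-blind mITT model does) and the empty category below 300 m.
- Use the mITT seeds already listed, and assign one of the three additional seed pairs to the mITT timed-function composite. The ITT composite also lacks a row and needs a pair.
- Report mITT beside ITT, and state that the decision to lead with ITT was made after unblinding.

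The cost is SAP wording and one further set of supportive tables. No new data are needed.

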9.4.5.3 North Star Ambulatory Assessment

The NSAA consists of 17 activities, each scored as 0, 1, or 2. The sum of these 17 scores will be used to form a total score. This total score will be analyzed using the ANCOVA analysis method outlined for the primary efficacy variable, for both the mITT and ITT populations, at the end of the double-blind and open-label phases. A separate analysis for the open-label phase will evaluate changes in total score in subjects with a baseline 6MWD ≥ 400 meters and < 7 years of age. Transformation of the total score to a linear scale [Mayhew 2013a] also will be performed. In addition, the odds of losing one or more of the NSAA items (score of 1 or 2 at baseline transitioning to a 0 score post-baseline) will be evaluated for ataluren versus placebo subjects using a risk ratio derived via re-sampling based analysis methods; the “lifts head” item will be excluded from this analysis because it does not fit the original construct of the NSAA based on Rasch analysis [Mayhew 2013a].

9.4.7 Safety

Vital sign results, including height and weight, will be summarized by treatment group, and by double-blind and open-label phases. Physical examination results will be listed. AEs will be classified using MedDRA, according to system organ class and preferred term. The severity of AEs will be graded according to the latest version of the CTCAE whenever possible. A treatment-emergent adverse event (TEAE) is defined as an AE that occurs or worsens in the period extending from the first dose of study drug to 4 weeks after the last dose of study drug in this study. The incidence of subjects experiencing specific TEAEs will be tabulated by treatment group, and by double-blind and open-label phases. Subjects experiencing the same event more than once will be counted only once. AEs will be summarized by worst CTCAE grade. AEs classified as CTCAE Grade 3 or higher, study-drug-related events, renal events leading to special diagnostic evaluations, events leading to discontinuation from treatment, and SAEs will be considered with special attention. Hematological data, serum biochemistry, and urine data will be summarized by treatment group, and by double-blind and open-label phases. Values will be graded according to CTCAE severity grade, when applicable. For variables graded according to CTCAE severity grade, the incidence of the worst severity grade observed will be displayed. For parameters for which a CTCAE scale does not exist, the frequency of subjects with values below, within, and above the normal ranges will be summarized by treatment group, and by double-blind and open-label phases. ECG data will be summarized by treatment group, and by double-blind and open-label phases.

9.4.8 Pharmacokinetic analyses

Plasma concentration collected at the last visit (Week 144) will be summarized with descriptive statistics (eg, n, arithmetic mean, standard deviation, standard error, median, minimum, and maximum, CV% mean, geometric mean, and CV% geometric mean). Additionally, the SAP will be developed to include evaluation of correlation between plasmatic concentrations of ataluren and 6MWD and TFT, including time to run/walk 10 meters, time to 10% worsening in 6MWD and other outcomes that are sufficiently sensitive.

9.5 Description and Timing of Analysis

When all subjects have completed the study and data entry is complete, the database will be locked, archived, unblinded, and analyzed.

10 OBLIGATIONS OF THE INVESTIGATOR AND THE SPONSOR

10.1 Compliance with Ethical and Regulatory Guidelines

The investigator is responsible for ensuring that the clinical study is performed in accordance with the Declaration of Helsinki and the International Council for Harmonisation (ICH) GCP guidelines.

10.2 Institutional Review Board/Independent Ethics Committee

Prior to enrollment of subjects into the study, as required by regulatory authorities, the protocol and informed consent document will be reviewed and approved by an appropriate IRB/EC. By signing the protocol, the investigator assures that approval of the protocol will be obtained from the IRB/EC and that all aspects of the IRB/EC review will be conducted in accordance with current regulations. Amendments to the protocol will be subject to the same IRB/EC review requirements as the original protocol. Only changes necessary to eliminate apparent immediate hazards to the subjects may be initiated prior to IRB/EC approval. In that event, the investigator must notify the IRB/EC and PTC Therapeutics in writing within the timeframe defined by local regulations. The investigator will also promptly notify the IRB/EC of any serious, unexpected AEs, or any other information that may affect the safe use of the drug during the course of the study.

A letter documenting the IRB/EC approval and a list of the names and titles of the IRB/EC members must be received by PTC Therapeutics prior to the initiation of the study. All correspondence with the IRB/EC should be retained in the investigator's study file.

The investigator shall submit a progress report, at least once yearly, to the IRB/EC, and must provide a copy to PTC Therapeutics. As soon as possible after completion or termination of the study, the investigator will submit a final report to the IRB/EC and to PTC Therapeutics. This report should include the dates of initiation and completion of the study, a description of any changes in study procedures or amendments to the protocol, any deviations from the protocol, the number and type of subjects evaluated, the number of subjects who discontinued (and the reasons for discontinuation), the number of subjects who completed the study, and the results of the study, including a description of any AEs. PTC Therapeutics will assist the investigator in the preparation of this report, as needed.

10.3 Informed Consent/Assent

By signing the protocol, the investigator assures that informed consent/assent will be obtained from each subject and/or parent/legal guardian prior to performing any study-related activities and that the informed consent/assent will be obtained in accordance with current regulations.

The investigator, or a sub-investigator listed on the Statement of Investigator Form FDA 1572, will give each subject and/or parent/guardian full and adequate verbal and written information regarding the objectives and procedures of the study and the possible risks involved. An informed consent/assent document will be provided to each subject and/or parent/guardian in a language in which the subject or parent/guardian is fluent. This information must be provided to the subject or parent/guardian prior to undertaking any study-related procedure. Adequate time should be provided for the subject and/or

parent/guardian to read the informed consent, to understand the risks and benefits of participating in the study, and to ask any questions that the subject and/or parent/guardian may have about the study. The subject and/or parent/guardian should be able to ask additional questions as and when needed during the conduct of the study. The subject's and/or parent(s)/guardian signature (as required by local regulations) on the informed consent form should be obtained at the investigator site in the presence of the investigator or a qualified representative (eg, sub-investigator). Where applicable, the subject will sign an age-appropriate assent form.

Each subject or parent/guardian will be given a copy of the signed consent/assent form. The original signed informed consent forms will be retained by the investigator with the study records.

The written subject information must not be changed without prior approval by PTC Therapeutics and the IRB/EC.

10.4 Electronic Case Report Forms

An eCRF is required and must be completed for each subject, with all required study data accurately recorded such that the information matches the data contained in medical records (eg, physicians' notes, nurses' notes, clinic charts, and other study-specific source documents). The eCRFs exist within a web-based EDC system managed by the data management contract research organization (CRO) for this study. After the investigator or the investigator's designees (eg, research coordinators) have been appropriately trained, they will be given access to the EDC system and will enter the data required by the protocol into the EDC system. Any change of data will be made via the EDC system, with all changes tracked by the system to provide an audit trail.

With an electronic signature, the investigator certifies that the data are complete and accurate prior to database lock. This electronic signature serves to attest that the information contained in the eCRFs is true. After database lock, the investigator site will receive a CD-ROM and/ or paper copies of the subject data for archiving at the investigator site. At all times, the principal investigator has final responsibility for the accuracy and authenticity of all clinical data entered onto the eCRFs and/or reported to PTC Therapeutics from the investigator site.

